sites³⁷ during regular medical visits, and written informed consent is obtained. A medical data form is submitted online by site personnel to enrol participants. After completion of online registration, an automated welcoming email is sent to participants with instructions for activating their SPIN account and completing SPIN Cohort measures online. SPIN Cohort participants complete online assessments upon enrolment and at 3-month intervals. To date, over 2000 SSc patients from 47 centres have been enrolled in SPIN's web-based cohort (currently approximately 1800 active participants).³⁷ Upon enrolment in the SPIN Cohort, all participants have consented to be contacted about SPIN sub-studies.

SPIN Cohort participants who complete measures in English or French will be invited by email and by popups during visits to the SPIN Cohort online assessment portal to enrol in the SPIN-COVID-19 Cohort, a sub-cohort of the SPIN Cohort. Additionally, recruitment announcements for the SPIN-COVID-19 Cohort will be posted on SPIN's Facebook page and Twitter account and distributed for posting via SPIN's patient organization partners in countries with large English and French-speaking populations, including Canada, the United States, France, the United Kingdom, Australia, New Zealand, and the Philippines. Recruitment announcements for the SPIN-COVID-19 Cohort will direct potential participants to an online Qualtrics web page where they will be provided with information about the SPIN-COVID-19 Cohort and have the opportunity to consent to participate or decline. SPIN Cohort participants who consent to participate will provide their SPIN username (email address linked with their SPIN account) to link to SPIN Cohort demographic and medical data.

Potential participants who are not SPIN Cohort participants will be asked to confirm that they are ≥ 18 years old, have been classified as having SSc by a physician, and are fluent in English or French. Eligible participants will be directed to set up a SPIN-COVID-19 Cohort user account and will provide basic demographic and disease-related information. All SPIN-COVID-19 Cohort participants will be invited to complete measures at baseline and every two weeks for

the duration of the COVID-19 pandemic. They will receive email reminders to complete bi-weekly follow-up assessments.

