Recruitment material for the SPIN-COVID-19 Cohort will state that a lottery will be held as an incentive. Three SPIN-COVID-19 participants who complete all scheduled assessments will be randomly selected to win a free trip to a SSc patient congress in 2021. This type of incentive has been used successfully in previous SPIN sub-studies.³⁸

SPIN-CHAT Trial Participants

SPIN-COVID-19 Cohort participants will be eligible for the SPIN-CHAT Trial if they (1) have a PROMIS Anxiety 4a v1.0¹⁸⁻²⁰ T-score ≥ 55 ; (2) do not report that they have had a positive test for the COVID-19 virus; and (3) report that they are not currently receiving mental health services, such as counselling or psychotherapy, during the COVID-19 outbreak. Cohort participants who were receiving these services at any time prior to the COVID-19 outbreak will be eligible for the trial if they are not currently accessing the services. Participants who are taking medications for a psychiatric disorder or symptoms will be eligible if they meet all other eligibility criteria. Participants will be eligible for enrolment if they meet eligibility criteria at any assessment, for the duration of trial enrolment. Consistent with the pragmatic nature of the trial, no additional exclusions will be applied.

Recruitment and Enrolment

Participants eligible for the SPIN-CHAT Trial will be provided with a brief description of the trial in the SPIN-COVID-19 *Qualtrics* platform immediately after completing their Cohort measures and will be asked if they would be interested in participating in the trial. Those who express interest will be provided with an online version of the trial consent form, which they can also download, and will be given the options of (1) consenting to participate; (2) declining participation; or (3) requesting that a member of SPIN's research team call them to answer questions they have about participating in the trial before consenting. Unless participants decline participation, they will be asked to provide information on days and times of day when

they could take part in videoconference sessions and their language preferences for sessions, including (1) only English; (2) only French; (3) either English or French; (4) preferably English, but comfortable in French; or (5) preferably French but comfortable in English.

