In addition to describing the study, the consent form will explain (1) that eligible participants who enrol will be randomly selected on a rolling basis to be included in the trial whenever there are enough participants enrolled to form additional intervention groups on particular days and times in English or French; (2) that those randomly selected will be randomly assigned to an intervention group or to the waitlist with a 1:1 allocation ratio; (3) that participants randomised to the SPIN-CHAT Program plus those allocated to the waitlist will complete measures online every two weeks as they would anyway as SPIN-COVID-19 Cohort participants; (4) that, depending on the number of participants who enrol with availabilities based on language, days, and times, it is possible that some enrolled participants will not be randomised; and (5) that, enrolled participants who do not receive the intervention as part of the trial, either because they are selected for the waitlist or because they are not selected for the program or the waitlist, will be offered the program post-trial if still relevant, pending development of the COVID-19 situation. A member of the SPIN research team will call all potential participants to confirm eligibility, day and time availability, and desire to participate in the trial, prior to completing enrolment.

Random Selection and Allocation

SPIN-COVID-19 Cohort participants who provide consent for participation will be entered into different pools based on their availabilities and taking into consideration time zone differences. Figure 1 illustrates the flow of participants into the trial, and Figure 2 the schedule of enrolment, interventions, and assessments. Once there are enough participants to complete an intervention group and assign an equal number of participants to waitlist control, a third-party randomisation service will randomly select eligible participants and randomly assign selected

participants to the intervention group or waitlist control. This process will be repeated until trial enrolment is complete.

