Participants may choose to discontinue their participation in the sessions at any time. We do not envision the need to modify the intervention or intervention assignment for any participants or to discontinue their participation in the program. However, if acute mental health concerns are disclosed to group moderators or other study personnel or if group moderators identify reasons to be concerned, these will be discussed immediately with the supervisor of group moderators and trial leadership. As appropriate, recommendations will then be made to participants to obtain support, and trial participation may be ended.

Participants assigned to the waitlist will receive notices and reminders to complete trial measures as part of the SPIN-COVID-19 Cohort. They will be contacted with information on intervention groups post-trial.

Trial Outcomes

The primary outcome analysis will compare PROMIS Anxiety 4a v1.0 scores between participants randomly assigned to the SPIN-CHAT Program versus the waitlist control at the end of the 4-week intervention period. The 4 items of the scale ask participants, in the past 7 days, how often: (1) “I felt fearful”; (2) “I found it hard to focus on anything other than my anxiety”; (3) “My worries overwhelmed me”; and (4) “I felt uneasy”. Items are scored on a 5-point scale (range 1-5), and response options include “never”, “rarely”, “sometimes”, “often”, and “always”. Higher scores represent more anxiety. Total raw scores range from 4 to 20 and are obtained by summing item scores for each domain. Raw scores are converted into T-scores standardized from the general US population (mean=50, standard deviation=10). PROMIS Anxiety 4a v1.0 has been validated in SSc.^{68,69} PROMIS Anxiety 4a v1.0 domain scores have been shown to be sensitive to change, and minimally important differences have been estimated to be between 2.3 and 3.4 T-score points.⁷⁰⁻⁷³ The 4-item PROMIS Anxiety 4a v1.0 score has been found to be highly correlated ($r = 0.93$) with the 8-item version.⁷⁰ The scale is available in English and French.⁶⁹

Secondary outcomes include symptoms of depression (PHQ-8),²¹ stress (PSS),²² loneliness (ULS-6),²³ boredom (MSBS-8),²⁴ physical activity (IPAQ-E),²⁵ and frequency of social interactions.

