Effects of short anxiety-focused interventions in post-disaster settings are between 0.40 and 0.80 standardized mean difference (SMD).^{87,88} This is larger than estimated minimally important difference for the PROMIS Anxiety 4a v1.0 score (SMD = 0.23 to 0.34 SMD).⁷⁰⁻⁷³ For an assumed effect size of SMD = 0.50, a two-tailed test with $\alpha = 0.05$, and an intra-class correlation coefficient (ICC) of 0.05, N=146 provides $\geq 80\%$ power for our primary outcome, PROMIS Anxiety 4a v1.0; assuming 25% dropout, we will recruit 195 participants (98 in 12 SPIN-CHAT groups; 97 in the waitlist). We believe that this is a conservative power and sample size estimate. First, in cluster RCTs, ICC values for individual patient outcomes are typically lower than our 0.05 estimate.⁸⁹⁻⁹¹ If the true ICC is lower than our 0.05 estimate, this will result in greater power than estimated. Second, there has been no loss to follow-up in the feasibility trial or initial waves of our full-scale trial of the videoconference-based SPIN support group leader program,^{48,49} which has a similar design. Thus, we believe that a 25% loss to follow-up may be conservative.

Data Collection and Management

Questionnaires for the SPIN-COVID-19 Cohort, including outcome measures for the SPIN-CHAT Trial (baseline, 2-week interim, post-intervention), will be completed using the online surveying tool *Qualtrics*. This method has been used in the SPIN support group leader training program feasibility and full-scale trials.^{48,49} Limits on eligible values that can be entered will be set to reduce erroneous entries. Data for SPIN Cohort participants will be linked to SPIN Cohort demographic and medical data via the email that is used to login to both the SPIN Cohort and SPIN-COVID-19 Cohort platforms. To ensure accuracy, we have embedded a check into the *Qualtrics* survey tool to ensure that emails entered by SPIN Cohort participants match their SPIN Cohort platform login. Once online survey data is collected, data will be exported to the statistics software program STATA. Checking and cleaning of the data will occur within SPSS and be done by members of the study team. All information obtained about the participants during this study will be treated confidentially within the limits of the law. To protect

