the participants' privacy, upon inclusion in the SPIN-CHAT Trial, a unique participant identification number will automatically be assigned to each participant. An encrypted database will be created, which will include the participant identification number and name. Data security measures in place at Qualtrics are described in the Qualtrics security statement.⁹² Information obtained from the survey and video recordings of the training sessions used to evaluate fidelity to program will be kept for 10 years on encrypted hard drives. During the trial, access to the data will be limited to the study investigators. Once trial results are reported, de-identified data will be made available upon reasonable request. No biological specimens will be collected.

Data Analysis

Analyses will be conducted by a statistician blind to trial arm allocation. For the primary outcome analysis (PROMIS Anxiety 4a v1.0), we will use an intent-to-treat analysis that compares all patients randomly assigned to the SPIN-CHAT Program to all patients assigned to the waitlist control. The intervention effect at 4 weeks will be estimated using a linear mixed model, adjusted for baseline PROMIS Anxiety 4a v1.0 scores. The model will include a random effect to account for clustering of participants in the training groups, but not for participants in the waitlist control arm, because there is no clustering in the control arm.^{26,27} We will investigate the effects of missing data using multiple imputation. As a secondary analysis, we will additionally adjust for age, sex, baseline loneliness, baseline boredom, and baseline physical activity. Analyses of secondary outcomes will similarly be done (1) controlling for baseline scores only and (2) controlling for baseline scores, age, sex, and other key baseline measures. Statistical significance for all analyses will be determined based on two-sided $\alpha = 0.05$. In addition, we will use complier-average causal effect analysis to estimate effects among patients who use the intervention at different levels compared to similar patients in the waitlist arm of the trial.⁹³

Data Monitoring

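### No stated analysis uses the 2-week PROMIS Anxiety score, although both arms provide it; modelling it alongside the 4-week score would be a cheap, modest improvement

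*Combined protocol and SAP*

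**What the plan says.** The Data Analysis section promises an "intent-to-treat analysis that compares all patients randomly assigned to the SPIN-CHAT Program to all patients assigned to the waitlist control". The model is given in one sentence: "The intervention effect at 4 weeks will be estimated using a linear mixed model, adjusted for baseline PROMIS Anxiety 4a v1.0 scores". A random effect covers the training groups, in the intervention arm only. On missing data there is one further sentence: "We will investigate the effects of missing data using multiple imputation". The imputation variables, the handling of one-arm clustering, and whether imputation is the primary estimate or a check are not stated.

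The other analyses listed are a version with more baseline covariates, the secondary outcomes treated in the same way, and a complier-average analysis. None mentions a 2-week score.

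The score is nevertheless collected:
- Data Collection and Management lists "outcome measures for the SPIN-CHAT Trial (baseline, 2-week interim, post-intervention", and Figure 2 has a 2-week interim column.
- Recruitment and Enrolment applies this to both arms: "participants randomised to the SPIN-CHAT Program plus those allocated to the waitlist will complete measures online every two weeks as they would anyway".
- Eligibility needs a PROMIS Anxiety score, and the SPIN-CHAT Trial Participants section says: "Participants will be eligible for enrolment if they meet eligibility criteria at any assessment, for the duration of trial enrolment". So the scale belongs to the recurring cohort assessment.

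**The concern.** The stated aim is to compare everyone randomised. A model with one 4-week outcome per person takes nothing from people who lack that outcome. Some of them will have answered at 2 weeks, and that answer says something about where they were heading.

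What is at stake is mainly bias. If the people lost differ on the 2-week score, and differ in another way in the other arm, the 4-week-only estimate shifts. Imputation from baseline alone would shift with it, so a check of that kind could agree with the primary result while both are off. A smaller stake is precision.

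**Working it through.** **The plan's own figure.** Inputs from the Sample Size section: effect 0.50 SD, two-sided alpha 0.05, power 80%, ICC 0.05, 25% dropout. With clustering in one arm and m analysed per group:

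n per arm = [(1 + (m - 1) x 0.05) + 1] x ((1.960 + 0.842)/0.5)^2 = [2 + 0.05(m - 1)] x 31.40

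This gives 70.6, 72.2 and 73.8 per arm for m = 6, 7, 8, so totals of 142, 146 and 148. The stated 146 reproduces at m = 7, and 146/0.75 = 194.7, so 195.

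**People without a 4-week score.** 0.25 x 195 = 49; 0.10 x 195 = 20. The abstract gives 162 randomised instead of 195: 0.25 x 162 = 41 and 0.10 x 162 = 16. I show 10% as well because 146/0.90 = 162.2, and because the plan regards 25% as possibly conservative.

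**Bias, large sample (1,000,000 per scenario).** None of these drivers is in the documents except the 0.50 effect; all others are assumed:
- 2-week effect 0.25 SD
- correlations 0.6 (baseline to 2 weeks), 0.5 (baseline to 4 weeks), 0.7 (2 to 4 weeks)
- equal loss rates in the arms
- logistic loss, with the odds multiplied by 2.72 per SD worse on the 2-week score in one arm only

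Estimated benefit in SD, truth 0.50:

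| Loss; arm with the dependence | 4-week only | 2-week score used, all lost have one | 2-week score used, half do |
|---|---|---|---|
| 25%; intervention | 0.59 | 0.50 | 0.54 |
| 25%; waitlist | 0.41 | 0.50 | 0.46 |
| 10%; intervention | 0.54 | 0.50 | 0.52 |
| 10%; waitlist | 0.46 | 0.50 | 0.48 |
| 25%; both alike | 0.50 | 0.50 | not run |

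Further results:
- Imputation from baseline alone matches the 4-week-only column (0.587 and 0.410 at 25%).
- When half of those lost have a 2-week score, bias falls from 0.088 to 0.038 (25%, intervention arm), so 0.038/0.088 = 43% remains. If none has one, nothing is corrected.
- With odds x1.65 at 25% loss, the 4-week-only estimates are 0.55 and 0.45. With odds x2.72 at 5% loss, they are 0.52 and 0.48.
- Correlations of 0.4/0.3/0.5 or 0.7/0.6/0.8 give 0.42-0.58 at 25% and 0.46-0.54 at 10%.
- If loss depends on the 4-week score itself, in the intervention arm only, at 25% (odds x1.65 to x2.72): 0.60-0.66 for 4-week only, 0.57-0.62 with the 2-week score.

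**Size on the scale.** At SD 10, 0.09 SD is 0.9 T-score points and 0.04 SD is 0.4. Trial Outcomes puts the minimally important difference at 2.3 to 3.4.

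**Precision under random loss.** With d the share lost, f the share of those who have a 2-week score, and r the partial correlation of the two follow-up scores:

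variance ratio = (1 - r^2) + r^2(1 - d)/((1 - d) + d f)

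r = (0.7 - 0.6 x 0.5)/sqrt(0.64 x 0.75) = 0.577, so r^2 = 0.333. With f = 1: d = 0.25 gives 0.667 + 0.333 x 0.75 = 0.917, an SE about 4% smaller; d = 0.10 gives 0.967, about 2% smaller. This ignores clustering. Simulation at trial size with ICC 0.05 and 10 imputations gave 0.1579 to 0.1534 (3%) and 0.1555 to 0.1543 (1%).

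**Coverage at trial size** (1,500 runs each, odds x2.72 in one arm, nominal 95%). For 98 in 12 groups plus 97 at 25% loss: 91.5-91.9% for 4-week only, against 94.9-95.3% with the 2-week score imputed. For 81 in 10 groups plus 81 at 10% loss: 93.8-94.3% against 94.7-94.8%. These runs fixed the group variance at its true value, so the figures for imputation are optimistic.

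**The case against.** **The plan is silent, not exclusive.** A reader might infer that the plan rules out the 2-week score or imputes from baseline only. The text supports neither. It names no imputation variables and does not bar a larger role for imputation. Leaving an interim score out of a 4-week model is a defensible choice. This stands, so the point is an improvement and not an error.

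**The bias mechanism is assumed.** A reader might also infer that the primary result will be biased. The documents do not show that loss specific to one arm is likely. Intervention and Comparator says: "We do not envision the need to modify the intervention or intervention assignment for any participants or to discontinue their participation in the program" (it does allow trial participation to be ended after acute concerns). Questionnaires run through the cohort, separately from the sessions, and of cohort participants the plan says: "They will receive email reminders to complete bi-weekly follow-up assessments". The plan reports no loss so far in a similarly designed program. This stands too. On the other side, participants are unblinded, the arms differ in burden (twelve sessions against questionnaires only), and the sponsor itself allowed for 25% loss. Differential loss cannot be excluded in advance.

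**The correction may be partial.** It is tempting to read 0.50 as what the 2-week score delivers. That is the best case. It needs a 2-week score from everyone lost, and loss that depends on nothing later.

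**Cost.** Recruitment began on April 7, 2020, so a change to the primary analysis needs to be documented. The Ethics and Dissemination section requires a formal amendment for modifications that may affect study conduct; it does not list analysis changes explicitly.

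**Conclusion.** The point holds as a low-priority improvement. The 2-week score is collected in both arms, no stated analysis uses it, and using it brings the primary estimate closer to the aim of comparing everyone randomised.

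The benefit depends on three things the documents do not give: how many are lost, whether loss follows the 2-week score differently by arm, and how many of those lost answered at 2 weeks. In the harshest of the 2-week-dependent scenarios, the shift avoided is at most 0.09 SD, below the minimally important difference. At 10% loss it is at most about 0.04 SD. It is nil when loss rate and mechanism are alike in both arms, and the help is only partial when loss depends on the 4-week score. The precision gain alone would hardly justify the change. The case rests on low cost and a more credible missing-data assumption.

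**What to change.** Make the primary analysis a baseline-adjusted mixed model of the 2- and 4-week scores, with arm-by-time terms, the training-group random effect in the intervention arm only, and the contrast read at 4 weeks. Equivalently, include the 2-week score in the planned multiple imputation, done by arm and respecting the training groups. The first is simpler; both are sound. The 2-week score should enter as an outcome or imputation variable, not as a covariate in the 4-week model, because it is measured after randomisation and may already carry part of the effect.

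In addition:
- keep the 4-week-only model as a sensitivity analysis;
- define which bi-weekly cohort assessment counts as the 2-week score, relative to each group's start;
- report by arm how many participants have no score after baseline;
- settle and record the change before unblinded data are seen.

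Cost: no new data or visits, a short revision of the Data Analysis section, and whatever amendment step the ethics committee requires. The downside is a somewhat more complex primary model, with clustering in one arm estimated from about 10 to 12 groups.

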Physical activity (IPAQ-E)²⁵: The 4-item IPAQ-E is a short-form version of the full IPAQ⁸⁴ designed to assess physical activity over the last week, including time spent sitting, walking, and in moderate and vigorous physical activity.²⁵ Compared to other short-form versions of the IPAQ, the IPAQ-E has examples of exercise specific to older adults. The full IPAQ has excellent reliability and moderate validity across many different countries,⁸⁴ and the IPAQ-E has similar validity.²⁵ The IPAQ is available in English and French.⁸⁵

Frequency of social interactions: Frequency of social interactions with others inside and outside of the home will be measured with 4 separate items, including (1) “On a typical day in the last week, how many times did you have a social conversation over the phone or a videoconferencing platform with one person?” (response = number of times); (2) “On a typical day in the last week, how many times did you have a social conversation over a videoconferencing platform with multiple people at the same time?” (response = number of times; not including SPIN-CHAT sessions); (3) “On a typical day in the last week, how long did you spend enjoying conversations with other individuals in the home?” (response = time); (4) “On a typical day in the last week, how long did you spend enjoying activities with other individuals in the home?” (response = time). Items (3) and (4) will only be displayed to participants who live with at least another person in their household.

Client Satisfaction Questionnaire (CSQ-8)⁸⁶: An adapted version of the 8-item version of the CSQ-8 will be administered to participants assigned to the SPIN-CHAT Program post-intervention in order to better understand how satisfied participants are with the program.

Adverse Effects will be assessed by ongoing monitoring during the trial and by asking participants post-intervention to describe any adverse experiences or outcomes that may have occurred.

Sample Size

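### The 0.05 rule covers every secondary analysis, with two models per outcome, no stated deciding model, open covariates and no multiplicity control or exploratory label

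*Combined protocol and SAP*

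**What the plan says.** The protocol's Data Analysis section sets one decision rule: "Statistical significance for all analyses will be determined based on two-sided" alpha of 0.05. No other sentence restricts this to the primary outcome.

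For the primary outcome (PROMIS Anxiety 4a at 4 weeks) the main model is a linear mixed model adjusted for the baseline anxiety score. The fuller model is ranked below it and its covariates are named: "As a secondary analysis, we will additionally adjust for age, sex, baseline loneliness, baseline boredom, and baseline physical activity".

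For the secondary outcomes the plan says the analyses will be done similarly, (1) "controlling for baseline scores only and (2) controlling for baseline scores, age, sex, and other key baseline measures". Neither model is labelled as main, and the other key measures are not listed.

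The Trial Outcomes section names six domains: "Secondary outcomes include symptoms of depression (PHQ-8),²¹ stress (PSS),²² loneliness (ULS-6),²³ boredom (MSBS-8),²⁴ physical activity (IPAQ-E),²⁵ and frequency of social interactions". Two of them have no defined score. Social interaction "will be measured with 4 separate items": two are counts and two are durations, and the durations are shown only to people who live with someone. The IPAQ-E is described as a four-item short form, "including time spent sitting, walking, and in moderate and vigorous physical activity", with no total specified.

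The documents contain no multiplicity adjustment, no ordering of the secondary outcomes and no statement that they are exploratory.

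**The concern.** Taken literally, the rule calls any secondary result with p below 0.05 significant, in whichever model it arises. The chance of at least one false positive then grows with the number of outcomes, and a second model adds to it. Because the second model's covariates are open, that model could also be settled after the data are seen.

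The secondary outcomes are stated objectives of the trial. Participants are unblinded, the outcomes are self-reported and the comparator is a waitlist. The protocol says that no earlier trial has tested such a program and that it would be easy to adapt for other populations if effective. In that setting an isolated significant result for, say, loneliness or depression could be read as evidence that the program works, most of all if the anxiety result is null.

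**Working it through.** The plan states no error rate for the secondary outcomes, so there is no figure of its own to reproduce on this point. The Sample Size section gives its power figure for the primary outcome only.

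**Inputs from the protocol**
- Significance level: two-sided 0.05 for all analyses (Data Analysis).
- Secondary outcomes: 6 domains (Trial Outcomes), evaluated post-intervention.
- Models per secondary outcome: 2 (Data Analysis).
- Upper count if every item of the two unscored domains is tested: 4 scale scores + 4 IPAQ-E items + 4 social-interaction items = 12.

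**Assumptions (the documents give no correlations)**
- Correlation between the test statistics of different outcomes: 0 to 0.5.
- Correlation between the two models' statistics for the same outcome: 0.90 to 0.95.
- No effect of the program on any outcome.

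**Step 1. Six outcomes, one model, independent.**
- Any significant result: 1 − 0.95^6 = 0.265.
- Significant in the direction of benefit: 1 − 0.975^6 = 0.141. For a single test it is 0.025.

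**Step 2. Six outcomes, one model, correlated.** A simulation of 400,000 draws of six equally correlated normal statistics at correlation 0.5 gives 20.8% (either direction) and 10.4% (benefit). With Step 1, the ranges are about 21-26% and 10-14%.

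**Step 3. Six outcomes, either model counts.** One outcome tested in two models at 0.05 has a false-positive rate of 6.4% to 7.0% instead of 5%. Over six independent outcomes:
- 1 − (1 − 0.064)^6 = 0.33
- 1 − (1 − 0.070)^6 = 0.35

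The simulation agrees:

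| Outcome correlation | Model correlation | Either direction | Benefit |
|---|---|---|---|
| 0 | 0.95 | 33.1% | 17.9% |
| 0 | 0.90 | 35.4% | 19.3% |
| 0.5 | 0.95 | 25.9% | 12.9% |
| 0.5 | 0.90 | 27.9% | 14.0% |

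The ranges are therefore about 26-35% and 13-19%.

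**Step 4. Twelve outcomes, if the items are tested separately.**
- One model, independent: 1 − 0.95^12 = 0.460 either direction; 1 − 0.975^12 = 0.262 benefit.
- One model, correlation 0.5: 31.9% and 15.9%.
- Either model, outcome correlation 0 to 0.5: 39-58% and 20-35%.

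**Step 5. What control would look like.** Holm over six domains compares the smallest p-value with 0.05/6 = 0.0083, the next with 0.05/5 = 0.010, and so on up to 0.05. The chance of any false claim then stays at or below 5% whatever the correlations.

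**The case against.** The plan has one primary outcome at one time point with a named main model, and the sample size is set for it alone. The secondary outcomes are already called secondary, and nothing says that one of them could stand in for a null primary. Unadjusted secondary p-values are common practice. All of this stands: the primary error rate is untouched, and Holm adjustment is one option among several. What remains is that the plan attaches a significance rule to these outcomes and does not say that the results are only supportive.

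Three stronger readings are tempting, and the documents do not support them.

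- *A chance secondary benefit is likely.* The either-direction percentages count apparent harms as well. In the benefit direction, even twelve outcomes with either model counted reach only about 35% under the assumptions used here, and 24 fully independent tests would give 1 − 0.975^24 = 45.5%. The either-direction figure passes 50% only with twelve outcomes, weak or no correlation between them, and either model counted.
- *There is no lead model.* The word *similarly* follows directly on the primary-outcome plan, where the baseline-score model comes first, and the order is repeated. That implies a lead model without stating it. The plan also nowhere says that significance in either model is enough, so the two-model figures show what the wording permits, not what it prescribes.
- *There are twelve secondary endpoints.* The protocol lists six. Describing what the IPAQ-E items cover does not make each an endpoint, and although the social-interaction items are called separate, the analysis section does not say that each is tested. The gap is an undefined score in two domains.

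**Conclusion.** The point holds as a weakness in how secondary results will be claimed. It does not touch the primary analysis. On the fairest reading (six outcomes, the baseline-score model deciding), a program with no effect has about a 21-26% chance of at least one significant secondary result and a 10-14% chance of an apparent benefit, four to nearly six times the 2.5% of a single test (10.4/2.5 = 4.2; 14.1/2.5 = 5.6). The looser readings that the text leaves open raise this, but a false benefit does not become more likely than not. The ranges rest on assumed correlations of 0 to 0.5 between outcomes and 0.90 to 0.95 between models; stronger correlation between outcomes lowers them. The second model adds less than the number of outcomes does. Its larger weakness is that its covariates are not fixed. This should be corrected before analysis.

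**What to change.** Amend the Data Analysis and Trial Outcomes sections to say:

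1. For each secondary outcome the model adjusted for the baseline score only, model (1), decides. Model (2) is a sensitivity analysis, and its covariates are listed in advance, as they already are for anxiety.
2. The confirmatory two-sided 0.05 claim applies to the primary analysis only. Secondary outcomes are reported as estimates with 95% confidence intervals and labelled supportive or exploratory. If significance is to be claimed for any of them, it is judged on Holm-adjusted p-values over the six domains.
3. Physical activity (IPAQ-E) and social interaction each have one prespecified summary, with the single items reported descriptively. The social-interaction summary must say how it handles people who live alone, who are not shown two of the four items.

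The cost is a few sentences and the choice of two summary scores, with no new data. The downside is weaker claims for individual secondary outcomes, for which the plan reserved no power.
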